21.3.5.2 Secondary Endpoints

Efficacy as measured by:

- The percentage of subjects with Clinical Improvement (partial or complete resolution of signs and symptoms [total composite score ≤ 1 on the VSS Scale] with no additional antifungal therapy required based on investigator's judgment) at the TOC visit.
- The percentage of subjects with Clinical Cure (complete resolution of signs and symptoms [total composite score of 0 on the VSS Scale] with no additional antifungal therapy required based on investigator's judgment) at the TOC visit.
- The percentage of subjects with Mycological Eradication (negative culture for growth of *Candida* spp.) at the TOC visit.
- The percentage of subjects with both Clinical Cure and Mycological Eradication at the TOC visit.
- The percentage of subjects with Continued Clinical Success (sustained resolution of signs and symptoms in subjects who achieved Clinical Success at the TOC visit) at the FU visit.

- The absolute change in total composite VSS score from Baseline to the TOC and FU visits.

Safety and tolerability as measured by:

- Adverse events (AEs), vital signs, treatment discontinuation and safety laboratory tests.

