21.3.6.1 Study Visits

Baseline Visit (Day 1): Study Drug Dosing

Subjects who meet all criteria for this study will receive the first dose of study drug, oral ibrexafungerp 300 mg, at the site and will self-administer the second 300-mg dose at home, 12 hours (± 4 hours) after the first dose. At this visit, subjects will be provided with subject diaries to record the date and time of their second study drug dose and to rate their vulvovaginal symptoms of infection, AEs and concomitant medication use from the Baseline (Day 1) visit until the TOC visit (Day 11 ± 3).

TOC Visit (Day 11 [\pm 3]): Assessment of Efficacy

At the TOC visit (Day 11), treatment compliance will be evaluated, and subject diaries will be returned and reviewed. The investigators and the subjects will rate the signs and symptoms of infection, respectively, on the VSS Scale (see [Section 21.2](#) [Appendix B] of the Main Study).

If the baseline vulvovaginal signs and symptoms have not improved or have worsened, vulvovaginal samples for fungal culture, species identification and antifungal susceptibility testing will be obtained and sent to a designated central laboratory.

Additional vaginal samples will be obtained for a potassium hydroxide (KOH) testing by the local laboratory if symptoms persist or have worsened. An abbreviated physical exam, vital signs measurements and safety laboratory tests will also be performed.

Follow-Up (Day 25 [\pm 4])

At the FU visit, subjects will rate their symptoms of infection on the VSS Scale. Vulvovaginal samples for pH determination, KOH testing and fungal culture should be obtained if there is persistence or worsening of vulvovaginal symptoms. Only if symptoms are present, the investigator will perform a vulvovaginal examination to rate the subject's signs of infection.

Unscheduled Visits

Unscheduled visits should be conducted anytime that there is indication of persistence or worsening of symptoms or an adverse event. If there is suspicion of persistence or worsening of symptoms, subjects will be strongly discouraged from self-administering any treatment and will be instructed to visit the study center for a proper evaluation before initiating any new VVC treatment.

All visits

AEs and prior/concomitant medications will be assessed and documented at all visits.

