21.3.10.6 Vulvovaginal Samples

The following vulvovaginal samples will be collected during the study:

- **Sample for direct microscopic examination with 10% KOH:** A vulvovaginal sample for KOH testing by the local laboratory will be obtained for all subjects at

the Baseline (Day 1) visit. If the Baseline (Day 1) vulvovaginal signs and symptoms have not improved or have worsened at the TOC (Day 11) and FU (Day 25) visits, a vaginal sample should be obtained for KOH testing by the local laboratory. Vaginal samples for KOH should also be collected any other time that a subject experiences persistence or worsening of symptoms (i.e., at unscheduled visits, if needed). The sample will be assessed by a local laboratory or at the site by the investigator or a qualified designee.

The direct microscopic examination with KOH is intended for the visualization of yeasts. If the KOH test is negative, the investigator should consider other causes for the persistence or worsening of the symptoms.

- **Sample for fungal culture:** A fungal culture will be collected at the Baseline (Day 1) visit for all subjects. If the Baseline (Day 1) vulvovaginal signs and symptoms have not improved or have worsened at the TOC (Day 11) and FU (Day 25) visits, a vaginal sample should be obtained for fungal culture. Vaginal samples for culture should also be collected any other time that a subject experiences persistence or worsening of symptoms (i.e., at unscheduled visits, if needed). The sample will be processed by a central laboratory for species identification. Positive cultures will also be tested for susceptibility against ibrexafungerp, fluconazole and additional antifungal agents, as deemed appropriate based on validated methods..
- **Sample for vaginal pH:** To be collected at the Baseline (Day 1) visit for all subjects and at the TOC (Day 11) and FU (Day 25) visits if vulvovaginal signs and symptoms have not improved or have worsened. Samples for pH should also be obtained any time that a subject experiences persistence or worsening of symptoms (i.e., unscheduled visits if needed). The sample will be assessed at the site by the investigator or a qualified designee.
- **Sample for identification of other pathogens:**

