- Vulvovaginal specimens will be obtained at the Baseline (Day 1) visit for all subjects and at the TOC (Day 11) and FU (Day 25) visits if vulvovaginal symptoms have not improved or have worsened. Samples will be collected for pH determination and KOH testing as well as to rule out bacterial vaginosis and *Trichomonas vaginalis* (wet-mount or other, process locally at the site or at a local qualified lab). Testing for *Neisseria Gonorrhoeae*, *Chlamydia trachomatis* or *Herpes* virus may also be conducted if these pathogens are suspected (central laboratory). Samples for fungal culture should also be collected for processing at a central laboratory. Susceptibility testing will be done centrally for all positive cultures during the study. Samples should also be obtained any time that a subject experiences persistence or worsening of symptoms (i.e., unscheduled visits if needed).
- If a subject is actively menstruating at a study visit that requires a vaginal exam, the visit should be rescheduled as soon as the subject's period ends but in no case more than 7 days after the initially

Visit	Baseline (Treatment)	Test of Cure	Follow-up	Unscheduled Visits ^a
Day (allowable window)	Day 1	Day 11 (±3)	Day 25 (± 4)	
Study Procedures	scheduled visit.			

- g. Vulvovaginal examinations will be repeated at the FU visit only if the subject presents symptoms. Otherwise, no additional vulvovaginal examination will be conducted, or signs rated.
- h. Subjects will receive their first dose of study drug at the site at the Baseline (Day 1) visit and will be given study drug to self-administer their second dose at home. The two doses should be administered approximately 12 (±4) hours apart, preferably with or immediately after a meal.
- i. Subject diaries will be used to rate vulvovaginal symptoms of infection on the VSS Scale and record second dose of study drug details, adverse events and concomitant medication use.
- j. Conducted by the central lab.
- k. Recorded from the time the Informed Consent Form is signed in the Main Study.

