#### **13.4.4.1. Sample Size**

The primary endpoint of the study is the percentage of subjects with Clinical Success (at least 50% reduction from Baseline in the total composite VSS score with no additional antifungal therapy required based on investigator's judgment) at the TOC visit. As this is a single arm sub-study, a statement regarding the Clinical Success rate and 95% confidence interval will be produced. It is estimated that 60 subjects will be included based upon published fluconazole failure rates. With a study of this size, if the Clinical Success rate for ibrexafungerp were 50%, this would correspond to a 95% confidence interval spanning from 36.8% to 63.2%. Given it is expected that the Clinical Success for ibrexafungerp in subjects who have already failed fluconazole will be low as these subjects had already failed to respond, a sub-study of this size is appropriate to assess the efficacy of ibrexafungerp in this patient population.

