#### **13.4.8.1.1. Primary Analysis**

The primary efficacy analysis will be performed on the mITT set at the TOC visit. The number and percentage of subjects with clinical success at the TOC visit will be presented. The 95% confidence interval of the clinical success rate will be calculated using the method of Clopper and Pearson. Missing data for clinical outcome will be imputed using the NRI method described in Section 13.4.4.4. Additional summarizations will be performed by Candida Species of the baseline yeast, but not subject to formal statistical analysis.

The same analysis employing the same methods as for the primary analysis will be performed for the ITT set to assess clinical success at TOC visit. Missing data for clinical outcome will be imputed using the NRI method described in Section 13.4.4.4.

A sensitivity analysis using the mITT set will be performed where subjects with the imputed clinical outcome using the NRI method at TOC visit will be removed from the analysis.

Summary of the number and percentage of subjects with continued clinical success at the Follow-up (FUP) visit, which defined as continued clinical success in subjects who achieved Clinical Success at the TOC visit, will be provided based on the ITT, and mITT sets.

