#### **13.4.8.2.2. Mycological outcomes**

A summary with the number and percentage of subjects with mycological eradication (negative culture for growth of *Candida* species) at the TOC visit will be performed by *Candida* species of the baseline yeast and overall. The subjects with missing TOC visit data for the mycological outcome will be imputed as mycological persistence using the NRI method described in Section 13.4.4.4.

Mycological outcomes will be assessed at the specified visit according to the following definitions.

- **Mycological Eradication:** A subject with negative culture for *Candida* species without need for further antifungal treatment prior to the TOC visit. For subjects who are free of symptoms and have no vulvovaginal specimens obtained at the TOC visit, the subject will be considered as mycological eradication;
- **Mycological Persistence:** A subject with a positive culture for *Candida* species or use of additional vulvovaginal or systemic antifungal therapy prior to the TOC visit. For the subject who early terminated before TOC visit and received additional vulvovaginal or systemic antifungal therapy prior to the early termination visit, the subject is considered a mycological persistence.

The same analysis will be done for the percentage of subjects with mycological eradication (negative culture for growth of *Candida* species) at the FU visit. For subjects who are free of symptoms and have no vulvovaginal specimens obtained at the FU visit, the subject will be considered as mycological eradication at the FU visit.

The change of mycological outcomes will be summarized in shift tables comparing the testing results at TOC visit with those at FU visit.

The analyses for mycological outcome will only be conducted for the mITT set.

In addition, a summary table will be presented to include MIC range, mode, MIC50, and MIC90, based on the ITT and mITT sets by treatment group and geographical region (USA or Ex-USA) for the following MIC results from 2 different methods, CLSI and EUCAST, respectively:

- MIC results for SCY-078 and fluconazole (FLU) at 24 hours against *Candida* species isolates obtained at TOC visit;
- MIC results for SCY-078 and fluconazole (FLU) at 48 hours against *Candida* species isolates obtained at TOC visit.

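### Sub-study TOC mycology: uncultured women are scored from their symptoms, in opposite directions, so the eradication rate is biased by an unknown amount and sign

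*SAP*

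**What the plan says.** Protocol 21.3.5.2 names the endpoint and defines it by culture: "The percentage of subjects with Mycological Eradication (negative culture for growth of" *Candida*) at TOC. Protocol 21.3.14.5.1 likewise defines eradication as a negative culture and persistence as a positive one.

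The TOC visit text in Protocol 21.3.6.1 makes the culture conditional: "If the baseline vulvovaginal signs and symptoms have not improved or have worsened, vulvovaginal samples for fungal culture" are taken. Protocol 21.3.10.6 applies the same condition to both later visits ("vulvovaginal signs and symptoms have not improved or have worsened at the TOC (Day 11) and FU (Day 25) visits"). Footnote e of the schedule, in Protocol 21.3.11 and again in SAP Appendix S1, uses nearly the same condition, and both schedules mark the TOC culture as taken if needed.

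SAP 13.4.8.2.2 has two rules for a woman with no TOC culture. If she is free of symptoms and no specimen was obtained, she is classed as eradicated. Otherwise non-responder imputation (NRI) applies: "The subjects with missing TOC visit data for the mycological outcome will be imputed as mycological persistence using the NRI method". SAP 13.4.4.4 states the general rule that a missing categorical response at a visit is a non-response. The same analysis is planned at follow-up (FU).

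**The concern.** A woman who has improved but still has a symptom meets neither the TOC culture trigger nor the symptom-free rule. A fall in VSS score from 8 to 2 is an example: she attends TOC, is a Clinical Success on the primary endpoint, needs no specimen, and is scored as Mycological Persistence. Her culture is absent because of the sampling rule and not because she dropped out. Protocol 21.3.14.3 reserves failure for women with no TOC assessment, and she had one.

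The symptom-free woman is the mirror image: she is scored as eradicated with no culture either. Between them, the two rules turn a culture endpoint into a proxy for symptoms in every improved woman who is not swabbed. SAP 13.4.11 lists neither rule as a change from the protocol.

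The values feed the eradication rate overall and by species, and on a natural reading also the TOC-to-FU shift tables and the baseline cross-tabulation. No planned analysis exposes them. The sub-study's sensitivity analysis without imputed values (SAP 13.4.8.1.1) covers clinical outcome only, whereas the main study has one for mycology (SAP 8.2.2).

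**Working it through.** **1. The plan's own figure.** The plan gives no rate or precision for eradication. Its only sub-study figure concerns the primary endpoint at a 50% rate: "this would correspond to a 95% confidence interval spanning from 36.8% to 63.2" per cent. With 60 women ("It is estimated that 60 subjects will be included based upon published fluconazole failure rates") and the exact method of SAP 13.4.8.1.1 ("The 95% confidence interval of the clinical success rate will be calculated using the method of Clopper and Pearson"), 30/60 gives 36.81% to 63.19%. The figure reproduces. It confirms the size and the method but says nothing about eradication.

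**2. How the rules fall.** For women who attend TOC and have used no further antifungal:

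| Status at TOC | Culture required by the TOC text? | Result if no specimen |
|---|---|---|
| Symptom-free (*a*) | No | Eradication, by definition |
| Improved, still symptomatic (*b*) | No | Persistence, by NRI |
| Not improved or worse (*c*) | Yes | Persistence, by NRI |

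**3. Bias formula.** Suppose *a* and *b* are uncultured and *c* is cultured, with true eradication rates ea, eb and ec, and N = a + b + c.

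- Reported rate = (a + c·ec)/N
- True rate = (a·ea + b·eb + c·ec)/N
- Bias = reported − true = [a(1 − ea) − b·eb]/N

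The rate is understated only if b·eb exceeds a(1 − ea), that is, if (1 − ea)/eb is below b/a.

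**4. Illustration.** The documents give none of these quantities for the sub-study. For a rough split I use the Phase 2b 600 mg arm at Day 10 (Protocol 7.1). Clinical cure was 14 of 27 (52%), so a = 0.52 × 60 ≈ 31. Score 0 or 1 was 70%, so b = (0.70 − 0.52) × 60 ≈ 11, and c = 60 − 31 − 11 = 18. I assume eb = 0.5 and ec = 0.2. The reported rate is (31 + 3.6)/60 = 57.7%.

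| Assumed ea | True rate | Reported − true (points) |
|---|---|---|
| 1.0 | 66.8% | −9.2 |
| 0.9 | 61.7% | −4.0 |
| 0.8 | 56.5% | +1.2 |
| 0.7 | 51.3% | +6.3 |

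Break-even is (1 − ea)/eb = 11/31 = 0.355, or ea ≈ 0.82 when eb = 0.5. For this split, with ea from 0.6 to 1.0 and eb from 0.3 to 0.5, the cases tried run from −9.2 to +15.2 points. With fewer symptom-free women (a = 20, b = 25, c = 15) the same cases run from −20.8 to +0.8.

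**5. One rate for both groups.** Apply that arm's 63% eradication rate to *a* and *b* alike, using unrounded counts. The symptom-free rule adds 31.1 × 0.37/60 = +19.2 points. The NRI rule removes 11.1 × 0.63/60 = 11.7 points. The net is an overstatement of about 7.5 points. A uniform rate is crude, since symptom-free women may clear more often.

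**6. What the data could say by themselves.** In the split of step 4, the best case is (31 + 11 + 3.6)/60 = 76.0% and the worst case is 3.6/60 = 6.0%. So 57.7% could lie up to 18.3 points below the truth or 51.7 above it. The rate among cultured women is 3.6/18 = 20%, a rate in non-improvers.

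**The case against.** The strongest reply is that the gap may be small in practice. Protocol 21.3.10.12 lists fungal culture among the efficacy procedures without a condition. Footnote e of the sub-study schedule adds "Samples should also be obtained any time that a subject experiences persistence or worsening of symptoms". SAP 13.4.9.5 also ties sampling to persisting symptoms. A residual symptom can be read as persistence, and nothing bars a site from taking the swab. That stands: a reader might infer that the protocol excludes these women from culture, and it does not. The TOC-specific text simply does not require one.

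The wider wording does not close the gap, however. The footnote's own example is unscheduled visits. Protocol 21.3.6.1 conditions KOH testing on symptoms that persist but culture on failure to improve, so the two conditions differ within one visit description. Sites could reasonably differ on whom to swab.

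The second reply is that little depends on this: the endpoint is secondary, in an exploratory single-arm sub-study, and is only summarised (Protocol 21.3.14.5.2). The listing shows assessments not done as missing. Overall Outcome is not imputed, and a woman with a residual symptom is not a clinical cure whatever her culture shows. All of that limits the weight of the point. It does not make an unmeasured result a measured one.

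**Conclusion.** The point holds as a bias of unknown direction. For improved women without a specimen, SAP 13.4.8.2.2 replaces the culture with a presumption taken from symptoms: eradicated if symptom-free, persistent if not.

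A reader might infer that NRI makes the eradication rate too low. The documents do not support that, because the symptom-free rule in the same section pushes the rate up, and which effect is larger depends on quantities that the documents do not give. Errors that may partly cancel still do not make a valid estimate.

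No point estimate of the bias is supported, and the figures above only show that the sign can go either way. They rest on assumed eradication rates, on no improved woman being swabbed, and on a split from a different population: acute VVC with a score of 7 or more, against fluconazole failures scoring 3 or more. Scores of 0 or 1 only approximate the split. A residual 1 may be a sign and not a symptom, and improved women scoring 2 or more belong in *b* but are counted in *c*. Mycology is analysed in the mITT set, which needs a positive Baseline culture, so the denominator may be below 60.

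**What to change.** In SAP 13.4.8.2.2:

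- Limit NRI to women who missed the TOC visit or from whom a required specimen was not obtained.
- Put women who attended and needed no specimen in a separate category, *not cultured per protocol*, split into symptom-free and improved but symptomatic.
- Report the eradication rate with best-case and worst-case bounds (all uncultured women eradicated, then all persistent), with the uncultured counts beside it.
- Show the observed-culture rate as a sensitivity analysis only, as SAP 8.2.2 does for the main study, and label it as drawn mainly from non-improvers. It should not be the main estimate.
- Apply the same treatment at FU and in the by-species, shift and cross-tabulation tables.

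Separately, reconcile the TOC culture triggers in Protocol 21.3.6.1, 21.3.10.6, 21.3.10.12 and footnote e of the sub-study schedule, and align SAP 13.4.9.5 and Appendix S1 with the result.

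The cost is SAP wording and a few extra table rows. The real downside is that the rate becomes a range, which may be wide if few improved women are swabbed.

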21.3.7.1 Inclusion Criteria

Subjects must fulfill all of the following criteria to be eligible for admission to this study:

1. Subject meets the following criteria at Baseline (Day 1):
 - a. Failure to achieve a significant resolution of the signs and symptoms of the *Candida* infection (total composite score ≥ 3 on the VSS Scale).
 - b. Culture positive for *Candida* spp. in a vaginal sample collected at Screening (Main Study).
 - c. Normal vaginal pH (≤ 4.5)
2. Subject meets all other inclusion criteria in [Section 11.1](#) of the Main Study (except Inclusion Criterion No. 3a, requiring a total composite score ≤ 2 on the VSS Scale).

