#### **13.4.8.2. Secondary Efficacy Endpoints**

##### **13.4.8.2.1. Clinical Outcome – Clinical Cure**

A summary with the number and percentage of subjects with clinical cure at the TOC visit will be presented by Candida Species of the baseline yeast and overall. Clinical outcomes will be assessed at the TOC Visit (Day 11) according to the following definitions:

- Clinical cure: Complete resolution of signs and symptoms of vulvovaginal infection without need for further antifungal treatment and topical vaginal drug therapy for the treatment of vulvovaginal irritation/pruritus prior to or at the TOC visit. Specifically, for complete resolution, any sign or symptom should be absent (score = 0);
- Not clinical cure: No response to therapy or incomplete resolution of signs and symptoms or use of additional vulvovaginal or systemic antifungal therapy or topical vaginal drug

therapy for the treatment of vulvovaginal irritation/pruritus prior to or at the TOC visit. For the subject who early terminated before TOC visit and received additional vulvovaginal or systemic antifungal therapy or topical vaginal drug therapy for the treatment of vulvovaginal irritation/pruritus prior to or at the early termination visit, the subject is considered a not clinical cure.

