#### **13.4.8.2.3. Overall Outcome**

A summary with the number and percentage of subjects with clinical cure and mycological eradication (overall outcome) at the TOC visit will be performed by Candida Species of the baseline yeast and overall. The subjects who cannot determine the overall outcome at the TOC visit will be removed from the analysis and no missing data will be imputed for both clinical outcome and mycological outcome.

Overall outcomes will be assessed at the TOC Visit (Day 11) according to the following definitions:

- Overall Success: A subject with the achievement of both a clinical cure and mycological eradication;
- Overall Failure: A subject with either not clinical cure or mycological persistence.

The analyses for overall outcome will only be conducted for the mITT set. The overall outcomes will be listed with baseline species referenced aside in a listing.

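### Nested sub-study: counting symptom-free, uncultured subjects as Mycological Eradication makes Overall Success at TOC the same subjects as Clinical Cure under per-protocol sampling

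*SAP*

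**What the plan says.** **Definition.** Protocol 21.3.5.2 and 21.3.14.5.1 define sub-study Mycological Eradication by a negative *Candida* culture. They make no allowance for a subject without a culture.

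**Sampling.** Protocol 21.3.6.1 and 21.3.10.6 call for a TOC culture only if the baseline signs and symptoms are no better or are worse. Sub-Study Table 1 marks the TOC culture as conditional, and its footnote e words the condition in terms of symptoms alone. Protocol 21.3.10.12 lists fungal culture among the efficacy procedures but refers back to 21.3.10.6.

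**Classification.** SAP 13.4.8.2.2 adds to the eradication definition that, for subjects "free of symptoms and have no vulvovaginal specimens obtained at the TOC visit, the subject will be considered as mycological eradication". The same holds at follow-up: with "no vulvovaginal specimens obtained at the FU visit, the subject will be considered as mycological eradication at the FU visit". The section also says: "The subjects with missing TOC visit data for the mycological outcome will be imputed as mycological persistence using the NRI method".

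**Composite.** SAP 13.4.8.2.3 defines Overall Success as "A subject with the achievement of both a clinical cure and mycological eradication". Subjects whose overall outcome cannot be determined "will be removed from the analysis and no missing data will be imputed for both clinical outcome and mycological outcome".

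**Declared changes.** SAP 13.4.11 lists one change for the sub-study, the wording of clinical failure.

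**The concern.** Protocol 21.3.5.2 has a secondary endpoint that combines Clinical Cure with Mycological Eradication. A reader will take it as cure backed by a culture result, in women who have just failed fluconazole. Under the SAP rule and the protocol's sampling, no cured subject need contribute a culture at all.

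Elsewhere the documents do not equate clinical resolution with a negative culture. Main-study subjects are randomized at a VSS score of 2 or less, yet the main-study mITT set separately requires a negative Baseline culture. For the main study, SAP 8.2.2 uses the same label, Mycological Eradication, for a negative culture only and imputes missing results as persistence. One SAP therefore gives the label two meanings.

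At stake is what the sub-study can say about mycological response, and whether a reader of the summary tables can tell a culture result from an inference based on symptoms.

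**Working it through.** **1. The plan's own figure.** The only sub-study precision statement is a 95% interval of 36.8% to 63.2% for a 50% Clinical Success rate with 60 subjects. Clopper-Pearson for 30/60 (2.5% quantile of Beta(30, 31), 97.5% quantile of Beta(31, 30)) gives 36.81% to 63.19%. It reproduces and is not in dispute.

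**2. The chain of definitions.**
- Entry (Protocol 21.3.7.1) requires "Failure to achieve a significant resolution of the signs and symptoms of the" *Candida* infection, meaning a VSS total of at least 3.
- Clinical Cure (SAP 13.4.8.2.1) requires no added antifungal or topical therapy and all items at zero: "Specifically, for complete resolution, any sign or symptom should be absent (score = 0".
- A cured subject has therefore fallen by at least 3 − 0 = 3 points. She has improved and is not due a TOC swab under 21.3.6.1 or 21.3.10.6.
- She is symptom-free with no specimen, so 13.4.8.2.2 classes her as eradicated. The antifungal limb of persistence cannot apply, because cure already excludes it.
- Hence she is an Overall Success. Conversely, every Overall Success is a Clinical Cure by definition.

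**3. Enumeration.** Baseline total 3 to 18 (16 values) × TOC sign total 0 to 9 (10) × TOC symptom total 0 to 9 (10) × antifungal before TOC (2) × antifungal at TOC (2) × true culture (2) = 12,800 states. Of these, 16 × 2 = 32 are Clinical Cure. These are logical states, not frequencies.

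| Sampling and rule | Clinical Cure | Overall Success | Undetermined |
|---|---|---|---|
| Protocol trigger, SAP rule | 32 | 32 | 0 |
| Protocol trigger, SAP rule not applied | 32 | 0 | 32 |
| Culture in every subject | 32 | 16 | 0 |

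In the first row no cured state has a specimen, and the true culture never changes the outcome. In the third row the 16 culture-positive cured states become Overall Failures.

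**4. Numerators against percentages.** SAP 13.4.4.4 keeps subjects with missing clinical outcome as failures; 13.4.8.2.3 removes undetermined ones. Assume 30 cures among 60. With 3 subjects missing TOC, Clinical Cure is 30/60 = 50.0% and Overall Success 30/57 = 52.6%. With 6 missing, the figures are 50.0% and 30/54 = 55.6%. That gap comes from missing-data handling, not from culture.

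**5. Size.** Let q be the share of cured subjects whose culture would be positive. The documents do not give q. With nobody removed, the composite under full culture would be (C/N)(1 − q). For an assumed C = 30 and N = 60:

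| q (assumed) | Composite with full culture | Under the SAP rule |
|---|---|---|
| 0% | 30/60 = 50.0% | 50.0% |
| 10% | 27/60 = 45.0% | 50.0% |
| 20% | 24/60 = 40.0% | 50.0% |
| 40% | 18/60 = 30.0% | 50.0% |

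Sixty is a ceiling for the mITT set, which needs a positive Baseline culture.

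**The case against.** The strongest reply is that the cause lies in the protocol's conditional sampling, and that the SAP says openly in advance how it will handle the result. Plain NRI would label every unswabbed cured subject as persistent, which is worse. The by-subject listing in 13.4.8.2.6 shows tests not done as missing. The endpoints are secondary and exploratory, and Protocol 21.3.14.5.2 plans no formal analysis of them. All of this stands, and it makes the matter one of labelling and disclosure. It does not explain why the summaries have no cultured/uncultured split, or why 13.4.11 is silent.

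A reader might infer more than the documents support:
- *That the Overall Success and Clinical Cure percentages must be equal.* Only the subjects and numerators are; step 4 shows why the percentages can differ.
- *That no cured subject can have a culture.* A site may swab off protocol, and a positive result would then give Overall Failure. A subject who entered on signs alone has no symptom to improve, so footnote e taken literally could make her due a swab.
- *That Overall Success is known to be inflated.* If every cured subject were truly culture-negative, it would be right.
- *That stand-alone eradication is biased upward.* Improved but still symptomatic subjects without a swab become persistence by NRI, so the net direction is open.

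One could also argue that the no-imputation sentence in 13.4.8.2.3 overrides the rule in 13.4.8.2.2. Unswabbed cured subjects would then be removed and Overall Success would be about 0. Because the rule sits inside the eradication definition, classification is the natural reading, but the SAP should say so.

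**Conclusion.** The point holds within stated limits. Under the culture trigger in Protocol 21.3.6.1 and 21.3.10.6, and reading the SAP rule as a classification, Overall Success and Clinical Cure are the same subjects. The composite is not independent mycological confirmation. With C cures the reported numerator is C and, apart from the two exceptions above, none is culture-confirmed. The number with a truly negative culture lies between 0 and C, so the overstatement is between nil and the whole reported figure, and the documents cannot narrow it.

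The departure from the protocol's definition is real and undeclared. The sub-study primary endpoint (Clinical Success) uses no culture outcome and is unaffected; so is the main study. It should be corrected, but it does not threaten the trial's main conclusions.

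**What to change.** 1. **SAP 13.4.8.2.2.** Report eradication at TOC, and at follow-up where it is summarised, as culture-confirmed and presumed, with the numbers cultured and not cultured. Assign each subject to the first category that applies:
   - added antifungal before the visit, or positive culture: persistence;
   - negative culture: confirmed eradication;
   - early termination, or due a swab but none taken: persistence by NRI;
   - symptom-free, not due a swab, no specimen: presumed eradication;
   - any other unswabbed subject: not cultured, with a statement of how she counts in the overall rate.

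   State the same exception to NRI in 13.4.4.4.
2. **SAP 13.4.8.2.3.** Split Overall Success into culture-confirmed and presumed. State that presumed subjects are classified by 13.4.8.2.2 and are not removed as undetermined. Note that under per-protocol sampling the numerator is that of Clinical Cure and is not independent mycological confirmation.
3. **SAP 13.4.11.** List the departure from the protocol definition.
4. **Culture triggers.** Protocol 21.3.6.1, 21.3.10.6 and footnote e of Sub-Study Table 1 word the trigger differently (signs and symptoms against symptoms alone, lack of improvement against persistence). They must be reconciled, and the SAP should cite the reconciled wording for who is due a swab.

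Carrying the split into the species tables, the cross-tabulation and the "shift tables comparing the testing results at TOC visit with those at FU visit" is optional.

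The cost is a few SAP sentences and table rows plus a protocol clarification for item 4; no extra visits or samples are needed. The culture-confirmed figure will look less favourable and will come mainly from subjects who did not improve, which should be stated beside it.
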